#### Measured variables/Indices:

##### Session 1

- **Self-report questionnaires:**
  - **Valence, Arousal, Dominance:** participants responded to prompts asking “how [pleasant or unpleasant/ activated or deactivated/ submissive (without control) or dominant (in control)] do you feel right now.”
  - **Open ended feelings report:** Participants responded to the prompt, “Please write out in your own words how you feel right now. Please be as SPECIFIC and DESCRIPTIVE as possible about how you feel” using a free-text field.
  - **Sickness Symptoms** (Andreasson et al., 2018).
  - **Daily Health Behaviors:** Participants reported on exercise, sexual activity, and consumption of caffeine, cigarettes, other nicotine products, alcohol, and medications over the past 24-48 hours.
  - **Adapted Brief Pittsburgh Sleep Quality Index** (Sancho-Domingo et al., 2021; Gordon & Chen, 2016)
  - **RU-SATED Scale** (Buyssse, 2014).
  - **Interoception Sensory Questionnaire** (Fiene et al., 2018)
  - **Two-way social support Scale** (Shakespeare-Finch & Obst, 2011)
  - **Physical Health Questionnaire-9** (Kroenke et al., 2001)
  - **The Perceived Stress Scale** (Cohen et al., 1983)
  - **Friend Questions:** Participants were asked to indicate how long they had known their same-gender friend (who was enrolled to participate as an interaction partner at session 2), how long they had been friends with their same-gender friend, their relationship satisfaction with their same-gender friend, an inclusion of other in the self-scale (Aron et al., 1992) measuring perceived self-other overlap between them and their same-gender friend, and the extent to which they could rely on and count on their friend.
  - **Couples Satisfaction Index (CSI) scales** (Funk & Rogge, 2007)
  - **Revised Cheek and Buss Shyness Scale** (Hopko et al., 2005; Cheek, 1983)
  - **The Psychoticism Scale** (Eysenck et al., 1985)
  - **Revised UCLA Loneliness Scale** (Russell et al., 1980)
  - **Self-Construal Scale** (Park & Kitayama, 2014)
  - **The Experiences in Close Relationship Scale** (Wei et al., 2007)
  - **Positivity Resonance Scale (3-item version)** (Major et al., 2018)

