### 5. Analysis

**Transformations:** Cytokine measurements that were below the limit of detection for assay were replaced with the lower limit of detection value. Cytokine measurements that were detectable, but more than 3 standard deviations above the mean were winsorized and replaced with that value (i.e., *Mean + 3 SDs*). Then, values for IL-6, IL-10, IFN- $\gamma$ , and TNF- $\alpha$  were log-10 transformed. Inflammatory reactivity to the vaccine was computed as the change in log-transformed concentrations of circulating cytokines from pre- to post-vaccine.

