**AMENDMENT 1: Testing for basic differences in physical symptoms, affectivity, and social connection.**

**1. Variables used**

- Demographic data
- S2 daily health behaviors
- Circulating concentrations of inflammation at session 1 and session 2
- Sickness Symptom Questionnaire (SicknessQ)
- Physical Symptom Endorsements for “Fatigue” and “Muscle aches/pains”
- Modified Positive and Negative Affect Schedule (PANAS)
- Adapted 5-item brief Pittsburgh Sleep Quality Index
- 10-items assessing social disconnection

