**2. Analysis Plan**

**Statistical models:** Statistical models will assess 5 broad scientific aims.

**Scientific Aim 1: Inflammatory Cytokines.** To test whether treatment groups differed in circulating levels of pro-inflammatory cytokines following vaccine administration, we will run repeated-measures analyses of variance (RM-ANOVA; Winkens et al 2007). Inflammatory cytokines at both sessions will be treated as the criterion, session number (i.e., time) will be treated as a within-subjects predictor, and condition assignment (placebo vs. influenza vaccine) will be treated as a between-subjects predictor. RM-ANOVA models will be run separately for each of the four inflammatory cytokines assayed. Significance will be assessed at  $p<0.05$ . We hypothesize a significant interaction between condition and time on inflammation such that participants in the influenza condition will have higher levels of all four markers of inflammation than participants in the placebo condition at session 2 but not at session 1.

**Scientific Aim 2: Sickness Symptoms.** To test whether treatment groups differed in sickness symptoms following drug administration, we will complete a series of analytic steps:

1. Given that the Sickness Symptom Questionnaire (SicknessQ) has primarily been validated in samples treated with endotoxin (a potent inflammatory challenge), we will begin by conducting confirmatory factor analysis with 1 factor on scale items. Good model fit for CFA will be represented by  $RMSEA \leq .08$ ,  $CFI \geq .95$ , and  $TLI \geq .90$  (Hu & Bentler, 1999; Schreiber, Nora, Stage, Barlow, & King, 2006). We will then run t-tests to assess for group differences in overall sickness symptom scores. Significance for t-tests will be assessed at  $p<0.05$ .
2. We will also run separate two-tailed independent-samples t-tests to assess for group differences in individual sickness symptoms (i.e., each item of the SicknessQ). Significance will be assessed at  $p<0.05$ .
3. Finally, we will run two additional two-tailed independent-samples t-tests to assess for group differences in endorsements of two physical symptoms not included in the SicknessQ but commonly assessed when using this and similar methods (Eisenberger et al., 2009; Kuhlman et al., 2018): “*fatigue*” and “*muscle aches/pain*.” Significance will be assessed at  $p<0.05$ . Significance will be assessed at  $p<0.05$ .

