## BODY AND SOCIAL BEHAVIOR (BSB)

(NH) arousal affect, and negative low (NL) arousal affect respectively. PH, PL, NH, and NL will be computed using the Positive and Negative Affect Schedule (PANAS) word endorsements. Specifically, PH will be operationalized as the mean endorsement across items: *amused, determined, enthusiastic, excited, happy, inspired, proud, strong, active, and alert*. PN will be operationalized as the mean endorsement across items: *Angry, Irritable, Nervous, Scared, Upset, Afraid, Ashamed, Distressed, Frustrated, Hostile, and Jittery*. NL will be operationalized as mean endorsement across items: *bored, guilty, sad, and worn out*. PL will be operationalized as mean endorsement across items: *attentive, calm, interested, grateful, and relieved*. Significance for t-tests will be assessed at  $p<0.05$ .

**Scientific aim 4. Sleep.** We will run three two-tailed independent-samples t-tests to assess for group differences in the subsequent night's sleep following vaccine-administration. First, we will assess for group differences in that night's sleep as operationalized using an index of items adapted from the Brief Pittsburgh Sleep Quality Index. These five items assess five facets of sleep—quality, quantity, daytime dysfunction, latency, and nighttime awakenings—and will be combined into a “Sleep Quality Index.” Next, we will run two additional models testing for group differences in two facets, subjective sleep quality (1-item) and subjective quantity (1-item), separately. Significance for all t-tests will be assessed at  $p<0.05$ .

**Scientific Aim 5. Social Connection.** We will run a two-tailed t-test to assess for group differences in felt social connection. Social connection will be operationalized as averaged scores on 10-items assessing feelings of social disconnection. Significance for t-tests will be assessed at  $p<0.05$ .

**Scientific Aim 6: Models using continuous measures of circulating cytokines.** To assess evidence for dose-dependency effects between circulating cytokines and outcomes-of-interest (same outcomes described in scientific aims 2-5), we will conduct a series of linear regression models using data from only the subset of participants assigned to the influenza vaccine condition ( $n=52$ ). Models will be run separately for each outcome-of-interest and for each cytokine and will take the general form:

1.  $outcome_i = \beta_0 + \beta_1(\Delta \text{inflammation}) + \beta_2(BL \text{inflammation})$

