2.  $outcome_i = \beta_0 + \beta_1(\Delta \text{inflammation}) + \beta_2(BL \text{inflammation}) + \beta_3(ASAB) + \beta_4\left(\frac{\text{waist}}{\text{hip}}\right)$

\*Note that we will only control for baseline inflammation in models if baseline inflammation is significantly correlated with change in inflammation (Dalecki & Willits, 1991; Llabre et al., 1991; O'Connell et al., 2017).

Sensitivity analyses will also be run to assess whether results are robust when individuals are excluded who reported a diagnosis of depression ( $n=4$ ), took an SSRI the day of the session ( $n=4$ ), or who were non-compliant prior to study session 2 (3 participants drank alcohol and 5 participants took pain-killers). Sensitivity analyses will be run excluding groups one by one to maximize power.

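### Aim 6 regresses outcomes on cytokine change without the session-1 outcome, so a pre-existing cytokine-symptom link could be read as a dose-dependent vaccine response

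*Combined protocol and SAP*

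**What the plan says.** Amendment 1, section 2 (Analysis Plan), sets out Aim 6 as follows: "To assess evidence for dose-dependency effects between circulating cytokines and outcomes-of-interest (same outcomes described in scientific aims 2-5"). The analysis is confined to the vaccine arm, 52 people, with no placebo comparison. On the form of the analysis the plan states: "Models will be run separately for each outcome-of-interest and for each cytokine and will take the general form". Two printed equations follow. Model 1 has change in the cytokine and its baseline value. Model 2 adds sex assigned at birth and waist/hip ratio. A note under the equations makes the baseline term conditional: "we will only control for baseline inflammation in models if baseline inflammation is significantly correlated with change in inflammation".

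The predictor is defined in section 5 (Analysis) of the main pre-registration: "Inflammatory reactivity to the vaccine was computed as the change in log-transformed concentrations of circulating cytokines from pre- to post-vaccine".

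The outcomes are those of Aims 2-5. Aim 2, for example, is framed as "To test whether treatment groups differed in sickness symptoms following drug administration". It does not name the session, but only session 2 follows the injection. In section 4 (Variables), "Sickness Symptoms" appears in the session-1 list and is repeated at session 2. The adapted Brief Pittsburgh Sleep Quality Index is likewise in both lists. The modified PANAS, the fatigue and muscle-ache items and the social disconnection items are listed at session 2 only.

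No printed model uses a session-1 outcome. The sensitivity analyses only exclude participants, for a depression diagnosis, SSRI use or non-compliance.

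**The concern.** In Aims 2-5 the arms are randomised, so leaving out a baseline outcome costs precision but does not bias the comparison. Aim 6 lacks that protection: it drops the placebo arm and uses an observed quantity, cytokine change, as the exposure.

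Suppose people with a higher usual cytokine level also tend to report more symptoms. Adjusting for one noisy baseline cytokine reading does not fully remove the usual level, so the session-2 cytokine still carries information about it, and so does the change given baseline. The change coefficient can then differ from zero even if nothing evoked by the vaccine affects symptoms. Because the plan calls the predictor vaccine reactivity and looks for dose-dependency, such a coefficient could be reported as a mechanism. A collected session-1 score would absorb much of this for two of the instruments.

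**Working it through.** **The plan's own figure.** The Power section of Amendment 1 gives a detectable f² of 0.16 for one coefficient (n=52, 4 predictors, two-sided alpha 0.05, power 0.80). Using the noncentral t with ncp = √(f²·n) and df = 52 − 4 − 1 = 47, the minimum f² is 0.157, which rounds to 0.16. Power at f² = 0.16 is 80.7%. The figure reproduces.

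**Set-up for the bias (assumed, not in the documents).** Cytokine: C1 = Tc + e1 and C2 = Tc + e2 + V, where Tc is the stable level. C1 has variance 1, the retest correlation without V is r, and V is the vaccine-evoked change with SD 0.5, so Var(C2) = 1 + 0.25 = 1.25. Symptoms: Y1 = Ty + f1 and Y2 = Ty + f2, with variance 1 and retest s. V has no effect on Y2. Tc and Ty correlate at t, so the cytokine-symptom covariance is c = t·√(r·s), the same at both sessions. The only related input in the documents is the 0.5 correlation between repeated measures in the sample size rationale; I use it as one anchor for r.

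**Change coefficient with baseline cytokine in the model.** It equals the coefficient of C2 given C1:

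b1 = (c·1 − c·r) / (1·1.25 − r²) = c(1 − r)/(1.25 − r²)

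- r = 0.5, s = 0.7, t = 0.5: c = 0.5·√0.35 = 0.296; b1 = 0.296·0.5/1.00 = 0.148 (simulated mean 0.147).
- r = 0.7, s = 0.7, t = 0.5: c = 0.5·0.7 = 0.350; b1 = 0.350·0.3/0.76 = 0.138.

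The true effect is zero in both cases.

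**Change coefficient without baseline cytokine.** Cov(Y2, C2 − C1) = c − c = 0. A pure level-to-level link cancels.

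**How often the plan's rule keeps baseline cytokine.** The correlation of C1 with change is (r − 1)/√(2.25 − 2r): −0.5/√1.25 = −0.447 at r = 0.5, and −0.3/√0.85 = −0.325 at r = 0.7. At n = 52, significance needs about 0.273 in absolute value. The simulated rule kept the term in about 93% of datasets at r = 0.5 and about 66% at r = 0.7.

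**False-positive rate for the change coefficient** (model 1 form, n = 52, nominal 5%, the plan's conditional rule applied):

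| Cytokine retest r | Symptom retest s | Trait correlation t | Plan's rule | Plus session-1 score |
|---|---|---|---|---|
| 0.5 | 0.7 | 0 | 5.0% | 5.4% |
| 0.5 | 0.7 | 0.3 | 9.1% | 5.5% |
| 0.5 | 0.7 | 0.5 | 18.8% | 7.4% |
| 0.7 | 0.7 | 0.5 | 11.1% | 6.4% |
| 0.5 | 0.8 | 0.6 | 30.0% | 8.1% |

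A rerun of the last row gave just under 29%, hence about 28-30% for the strongest link. With the score added, the rate reaches about 10% when symptom retest is only 0.5. In the r = 0.5, s = 0.7, t = 0.5 case with baseline cytokine always in the model, the added score lowers mean b1 from 0.147 to 0.051.

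**Weak links.** With baseline cytokine always in the model and s = 0.7, rejection is 5.5% (r = 0.5) and 4.9% (r = 0.7) at t = 0.1, and 6.6% and 5.5% at t = 0.2.

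**Cost of the extra term.** With 5 predictors (df 46), power at f² = 0.16 is 80.6%.

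**The case against.** The strongest reply is that nothing in the documents shows a stable cytokine-symptom link in this sample. That is correct. With a trait correlation of 0 to 0.2 the plan's rejection rate stays near nominal, so a reader who infers that Aim 6 will mistake such a link for a vaccine effect goes beyond the documents. They support only that it could.

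The conditional rule also helps. A reader of the two equations alone might think that baseline cytokine is always adjusted for; the note beneath them says otherwise. When the term is dropped, a pure level link cancels. At cytokine retest 0.85 the rule kept the term in only about 30% of runs, and rejection at trait correlation 0.3 was 4.7%. At retest 0.5, however, the term almost always stays, so the rule narrows the concern without removing it. Bias after the term is dropped would need vaccine reactivity itself to be tied to symptom reporting, a further assumption that is not in the range given here.

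Model 2's covariates and the exclusions for depression and SSRI use may take out part of a stable link. They were not simulated, and I count them as partial protection.

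It is also tempting to say that every SicknessQ item model is seriously exposed and that the session-1 item would cure it. Single items may be unstable. With symptom retest 0.3, trait correlation 0.3 and cytokine retest 0.5, rejection was 6.6% without the session-1 score and 6.1% with it, so there is little bias there and little gain.

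**Conclusion.** The concern stands in conditional form. The omission is plain on the page, the exposure is not randomised, and the baseline-cytokine term does not close the gap when it is used. A pre-existing link could therefore pass as dose-dependency. Under trait correlations of 0 to 0.6 and cytokine retest of 0.5 to 0.7, with an SD of 0.5 for the vaccine-evoked change, the false-positive rate under the plan's rule is about 5% to about 28-30%. The session-1 score brings it to about 5-10%. All of these correlations are assumptions, and the upper end needs the strongest link. The documents do not support a claim that the bias is present, that it affects all items alike, or that the randomised comparisons in Aims 2-5 are biased by the same omission. The change is still worth making, because the data exist and the cost is negligible.

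**What to change.** - In models 1 and 2, add the matching session-1 score as a covariate for the SicknessQ outcomes (total with total, item with item) and for the three sleep outcomes (index, quality, quantity).
- Base any dose-dependency statement for those outcomes on the adjusted change coefficient. State that one noisy baseline score reduces the bias without removing it.
- For PANAS affect, fatigue, muscle aches and social disconnection, report the Aim 6 results as associations within the vaccinated group and not as evidence of a vaccine dose response. Other session-1 scales could be tried as stand-ins, but nothing here shows that they would work.

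The cost is one residual degree of freedom at n = 52 (47 to 46 in model 2) and no new data.

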### Sample size:

**Sample size rationale:** A priori, we aimed to recruit 100 individuals (~50 females) ages 18-35. This sample size was selected based on a power-analysis conducted in G\*Power (Faul et al 2007) indicating that a minimum of 90 participants (45 per condition) were necessary to achieve 80% power to detect a medium effect size of  $F^2=.15$  for a within/between-subjects interaction (2 groups; 2 repeated measurements; 0.5 correlation between measures). We aimed to collect 100 instead of 90 in case of data loss due to, for example, participants not returning to the lab for their post-vaccine session.

**Stopping rule:** We concluded the study after reaching our target recruit goal (N=100), which happened to coincide with the start of the university's winter break, meaning clinics and services

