## BODY AND SOCIAL BEHAVIOR (BSB)

$n_{participants}=102$ ,  $r=0.5$ , suggested that we would be adequately powered to observe a medium effect size  $f^2=0.14$ .

Sensitivity Analysis for t-tests: Sensitivity analysis conducted in g\*power for a two-tailed t-test (independent means) with  $\alpha=0.05$ ,  $(1-\beta)=0.80$ ,  $n_1=50$ ,  $n_2=52$  suggested that we would be adequately powered to observe a medium effect size  $d=0.56$ .

Sensitivity Analysis for linear regression: Sensitivity analysis for simple regression (fixed model, single regression coefficient) for a two-tailed t-test with  $\alpha=0.05$ ,  $(1-\beta)=0.80$ ,  $n_{participants}=52$ , and  $n_{predictors}=4$  suggested that we would be adequately powered to observe a medium effect size  $f^2=0.16$ .

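### Aim 6 lets a significance pretest decide whether baseline cytokine is adjusted for, so the change slope can mean different things for different cytokines and can be biased either way

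*Combined protocol and SAP*

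**What the plan says.** Scientific Aim 6 of Amendment 1 relates cytokine change to each outcome of Aims 2-5, using "data from only the subset of participants assigned to the influenza vaccine condition", which is 52 people. Every pairing of an outcome with a cytokine gets its own regression. Model 1 contains change and baseline. Model 2 adds assigned sex at birth and waist-hip ratio. The note below model 2 then makes baseline conditional in both: "we will only control for baseline inflammation in models if baseline inflammation is significantly correlated with change in inflammation". It cites three methods papers.

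The Transformations paragraph of section 5 defines the exposure: "Inflammatory reactivity to the vaccine was computed as the change in log-transformed concentrations of circulating cytokines from pre- to post-vaccine". Baseline is therefore one of the two components of the change score.

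The note gives neither a significance level nor an analysis set for the pretest. The sensitivity analyses listed after it only exclude participants; none fixes the baseline adjustment one way or the other. The power statement for this aim ("Sensitivity analysis for simple regression (fixed model, single regression coefficient) for a two-tailed t-test with" α=0.05, 52 participants) uses four predictors, which is model 2 with baseline included.

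**The concern.** Omitting baseline leaves β1 unchanged only if baseline is unrelated to the outcome given change, or is uncorrelated with change. The pretest looks only at the second condition, and a non-significant correlation in 52 people does not show that it holds.

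The decision is made cytokine by cytokine. IL-6 could be reported as a slope at fixed baseline and TNF-α as a marginal slope on change, both presented as evidence of dose-dependency, although their coefficients would not be comparable. An exclusion-based sensitivity analysis could also flip the pretest, so that the model changes along with the sample.

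At stake are the size and comparability of the Aim 6 coefficients and the power to detect them. The randomised comparisons in Aims 1-5 are not affected.

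**Working it through.** **The plan's own figure.** Inputs from the Power section of Amendment 1: f²=0.16, n=52, 4 predictors, two-tailed α=0.05. With noncentrality λ = f²·n = 0.16 × 52 = 8.32 and 52 − 4 − 1 = 47 denominator df, power is .8065. The exact f² for 80% power is 0.157, which rounds to 0.16, so the stated figure is reproduced.

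**Pretest cut-off.** From r = t/√(n − 2 + t²), two-sided 5% (assumed):
- n=52: |r| > .273.
- n=49 to 47 (if all 3 participants who drank alcohol, or all 5 who took painkillers, were vaccinated and excluded): .282 to .288.
- n=102, if both arms were used: .195.

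**How often baseline survives.** With equal pre and post SDs and pre-post correlation r, corr(Δ, BL) = −√((1 − r)/2). This is −.50 at r=.5, −.316 at r=.8 and −.224 at r=.9. In simulation, baseline is kept in 97%, 64% and 36% of datasets. If four independent cytokines shared one r, the chance of a mix of adjusted and unadjusted models is 1 − p⁴ − (1 − p)⁴: 11% for p=.97, and 82% for both p=.64 and p=.36.

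**Direction of bias.** With baseline omitted without any pretest, E(β1) = β1 + β2·cov(Δ, BL)/var(Δ).
- Equal SDs: (r − 1)/(2 − 2r) = −½. With β1=β2=.60, the expected slope is .60 − .30 = .30.
- Post/pre SD ratio 1.25, r=.9: cov = 1.25 × .9 − 1 = .125 and var = 1.5625 + 1 − 2.25 = .3125. The ratio is +.4 and the expected slope is .60 + .24 = .84.

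The pretest limits the damage, because it omits baseline only when the sample correlation is small. Simulation shows what remains.

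**Simulation.** 20,000 datasets per scenario, n=52. BL ~ N(0,1); post = s(r·BL + √(1 − r²)·z); outcome = a·BL + b·post + e; Δ = post − BL. Hence β1 = b and β2 = a + b. The values of a, b, s, the residual SD and every r except .5 are assumptions, not figures from the documents. Always adjusting gave a mean β1 of .597-.603 in every scenario with b=.6.

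| Scenario (b=.6, residual SD .8 unless stated) | Baseline kept | Mean β1 under the rule | Power: rule vs always adjusting |
|---|---|---|---|
| Outcome follows session-2 level (a=0), r=.5 | 97% | .60 | .99 vs .99 |
| same, r=.7 | 82% | .57 | .90 vs .95 |
| same, r=.8 | 64% | .54 (.43 when dropped) | .71 vs .87 |
| same, r=.9 | 36% | .47 (.40 when dropped) | .35 vs .61 |
| same, residual SD 1.0, r=.8 | – | – | .57 vs .70 |
| same, residual SD 1.0, r=.9 | – | – | .26 vs .43 |
| Pretest on all 102, r=.8 | 91% | .59 | .83 vs .86 |
| Pretest on all 102, r=.9 | 61% | .54 | .48 vs .62 |
| SD ratio 1.25, r=.9 | 36% | .70 | .83 vs .80 |
| Weaker baseline effect (a=−.3), r=.8 | 64% | .57 | .82 vs .86 |
| same, r=.9 | 36% | .54 | .50 vs .61 |
| Outcome follows change (a=−.6), r=.8 | 64% | .60 | .87 vs .87 |
| same, r=.9 | 36% | .60 | .62 vs .61 |

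Repeat runs agreed to within about .01.

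**Type I error.** With no true slope and a baseline effect (a=.5, b=0, r=.8-.9), it is .056-.062 under the rule and .049-.053 when always adjusting. In a second parameterisation (true slope 0, standardised |β2|=.5) it is 4.4-6.0% overall, and up to about 9% among the datasets in which baseline was dropped.

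**The case against.** The strongest case against is about weight rather than arithmetic.

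- **The plan's own planning value shows no harm.** The only pre-post correlation in the documents is the "0.5 correlation between measures" of the sample size rationale, where the rule is harmless. This stands, but that value is an input to the repeated-measures ANOVA power calculation and is not given for any particular cytokine.
- **The headline scenario assumes the outcome follows the session-2 level.** If it follows change, there is no bias, and intermediate cases lose less. This also stands: the documents do not settle which applies.
- **Power can rise as well as fall.** It does at an SD ratio of 1.25 (.83 vs .80), but there the slope is overestimated, so the gain comes partly from bias.
- **The bias is small beside sampling error.** In the r=.7 to .9 cases it is .03 to .13, against a standard error of β1 of about .16 to .27. That is fair for a single coefficient. It does not make coefficients comparable across cytokines.
- **Both slopes are legitimate, and a rule blind to the outcome avoids choosing a model by its result.** True, but the plan prints one estimand and lets a pretest replace it for some cytokines.
- **The level and sample can be inferred.** Aim 6 is restricted to the vaccine arm and Amendment 1 uses p<0.05 elsewhere, so the reading with all 102 participants is strained. Agreed; the ambiguity is a minor part of the point.
- **The rule is prespecified and cited.** Prespecification does not give the pretest a consistent estimand, and the three cited papers were not available to check.

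**Conclusion.** The concern holds. Because of the note, β1 need not be the same quantity for all four cytokines, and relative to the baseline-adjusted slope in the printed equations it can be biased up or down.

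The size is conditional. It is negligible at pre-post r=.5 with equal SDs, or when baseline adds nothing to the outcome given change. It becomes material at correlations of about .7 and above when the outcome tracks the session-2 level: under the stated assumptions, the power difference is .95 − .90 = .05 at r=.7 and .61 − .35 = .26 at r=.9. Any rise in type I error is small overall, to about .06.

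This is a recommended improvement to a non-randomised, within-arm analysis, not a threat to the trial's group comparisons. Confidence is medium, because the cytokines' correlations, SDs and baseline effects are not in the documents.

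**What to change.** Delete the note and include baseline log10 cytokine in every Aim 6 model, for every outcome, every cytokine and every exclusion-based sensitivity analysis. Both printed equations already do this. If the marginal association with change is also of interest, report the change-only model for all four cytokines as a labelled sensitivity analysis. Since the plan records that the data had already been accessed, date the change and give the reason for it.

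The cost is one sentence and one degree of freedom. At f²=0.16 and n=52, power is .8065 with four predictors (47 df) and .8068 with three (48 df), a difference of .0003. The power statement already counts four predictors and needs no revision. In the simulated scenarios where the rule did no harm, always adjusting cost at most .006 in power.

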## **2. Design**

**Overview of Study design:** Participants completed two in-person study sessions ~24 hours apart. All study visits were scheduled in the morning (7:00 AM – 11:00 AM). During the first session (1-hour), participants completed informed consent, a self-report baseline questionnaire, and a heartbeat counting task. They also provided a baseline blood sample, collected via venipuncture, and were administered an injection of either the active influenza vaccine or a sham vaccine (saline solution). During the second session (2-hours), participants again completed self-report questionnaires and had their blood taken via venipuncture. They then completed three tasks: a sociogram task, two social interaction tasks, and a bargaining game task. Participants were then debriefed and compensated \$25/hour.

**Study type:** Experiment

**Randomization & Blinding:** Simple condition random assignment was implemented by UNC's Investigational Drug Services (IDS) pharmacy. Pre-filled (unlabeled) syringes were delivered by IDS to the University of North Carolina at Chapel Hill's Clinical and Translational research center (CTRC) in opaque stapled bags. These bags were opened by trained CTRC nursing staff—who dispensed the doses—immediately prior to drug injection. Primary research staff were not present for drug injection and participants were asked to look away during injection (and never saw the syringes) to maintain blinding.

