### **Explanation of existing data:**

- A combination of t-tests and chi-squared tests were conducted to assess for any failure in random assignment. Variables assessed included: Age, Assigned Sex at Birth (ASAB), Gender, Sexual Orientation, Race/Ethnicity, Annual Household Income, Subjective Socioeconomic Status, Depressive Symptoms, Perceived Stress, Sleep Health, menstrual status, use of birth control, waist-hip ratio, mental health diagnoses, use of mood-altering medications, baseline levels of circulating cytokines, and non-compliance with instructions to refrain from alcohol use taking OTC medications prior to study sessions.

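### Aim 6 checks confounding by depression only through two small exclusions, although a depressive-symptom score that could serve as a covariate was collected at session 1

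*Combined protocol and SAP*

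**What the plan says.** Amendment 1, section 2 (Analysis Plan), Aim 6 fits linear regressions in the influenza-vaccine arm only (n=52), one for each outcome and cytokine. Model 1 contains cytokine change and baseline cytokine. Model 2 adds sex assigned at birth and waist-hip ratio. Baseline cytokine is kept only if it correlates significantly with the change. Neither model contains a measure of depression.

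The sensitivity paragraph after Aim 6 excludes people who "reported a diagnosis of depression" (n=4), people who "took an SSRI the day of the session" (n=4), and people who were non-compliant before session 2 ("3 participants drank alcohol and 5 participants took pain-killers"). On how these are applied it says: "Sensitivity analyses will be run excluding groups one by one to maximize power". It does not say which session the SSRI flag refers to, how the two groups of four divide by arm or overlap, or which aims the checks cover.

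Elsewhere the protocol shows what else is available:
- Section 2 (Design): "All study visits were scheduled in the morning", between 7 and 11 AM.
- Section 3 (Explanation of existing data): the arms were compared on depressive symptoms and on "mental health diagnoses, use of mood-altering medications".
- Section 4 (Variables): session 1 includes the "Physical Health Questionnaire-9", whose cited source in the reference list is a depression severity measure. Both sessions record medications over the preceding 24 to 48 hours.

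**The concern.** Depressive symptoms at baseline could plausibly be related both to how much a person's cytokines change and to how that person reports mood, sleep, sickness and connection a day later. If so, an Aim 6 slope can arise with no dose-response effect of inflammation. Nothing in the design of Aim 6 rules this out, because everyone in it received the vaccine and cytokine change was not assigned.

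The planned exclusions address this only through narrow flags. The SSRI flag depends on whether a dose was taken on the day of a morning visit, so it can miss a regular user who doses afterwards. The depression flag depends on a reported diagnosis, so it ignores graded symptoms in everyone else. Each run removes at most four people. A slope that survives could be read as robust to depression when most of the variation in symptoms has not been touched.

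**Working it through.** **1. Reproduce the plan's figure.** Inputs from Amendment 1, Power: n=52, 4 predictors, two-sided α=0.05, 80% power, stated f²=0.16. For a single coefficient, df = n − p − 1 = 52 − 4 − 1 = 47 and the noncentrality is √(n·f²). Solving for 80% power gives f²=0.157 (noncentrality √(52 × 0.157) = 2.86). Power at f²=0.16 is 80.7%. The stated figure reproduces.

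**2. Cost of one more covariate.** With 5 predictors, df = 46 and the detectable f² is again 0.157 (0.1575 against 0.1574).

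**3. Cost of the planned exclusion.** Four people are 4/102 = 3.9% of the sample. If all four are in the vaccine arm (an assumption, since the split is not given), they are 4/52 = 7.7% of Aim 6. The detectable f² then rises to 0.171, and power at 0.16 falls to 77.3%.

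**4. What each check does about confounding.** The documents give no correlations, so these are assumed: symptoms correlate a = 0.3 to 0.4 with cytokine change and b = 0.5 to 0.6 with the outcome, with no cytokine-outcome link once symptoms are held fixed. The expected spurious correlation is a × b, from 0.3 × 0.5 = 0.15 to 0.4 × 0.6 = 0.24. Simulated results at n=52:

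| Analysis | Mean r | False positives |
|---|---|---|
| No check | 0.15 to 0.24 | 19% to 41% |
| Two of the eight highest scorers removed | 0.14 to 0.23 | 17% to 37% |
| Four highest scorers removed (best case for the exclusion) | 0.12 to 0.20 | 13% to 28% |
| Symptom score as covariate, all 52 kept | about 0 | about 5% |

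Even the best-targeted exclusion leaves about four fifths of the spurious correlation (0.12/0.15 = 0.80; 0.20/0.24 = 0.83). The simulation omits the other model 2 covariates and treats the score as an error-free measure of the confounder. With a noisy score, the covariate would remove only part of the bias.

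**5. Effect on the slope's precision.** If symptoms correlate a with cytokine change, the slope's standard error is multiplied by 1/√(1 − a²), before any gain from lower residual variance. That is 1/√0.91 = 1.05 at a=0.3 and 1/√0.84 = 1.09 at a=0.4.

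**The case against.** Four points can fairly be made for the plan.

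- **No unflagged person is shown to exist.** A reader might infer that exposed people do remain in the data. The documents give no count of SSRI users outside the four, or of participants with high symptom scores and no diagnosis. All that can be said is that the definitions allow such people to remain. Some of those missed by the SSRI flag may also be caught by the diagnosis exclusion, although the exclusions are not combined.
- **Removing four people can change a result.** A reader might infer that the checks are close to inert. They are not. In simulated Aim 6 analyses at f²=0.16 with all four in the vaccine arm, significance changes in about 7% of runs if the four are ordinary. It changes in 16% to 25% if they lie 1 to 2 SD away on both cytokine change and outcome. A changed result would be informative; an unchanged one says little.
- **Randomisation protects Aims 1 to 5.** Prior depression or SSRI use is not expected to bias the arm contrasts, and the arms have already been compared on these variables. This stands, and confines the point to Aim 6.
- **The plan claims little.** It asks only whether results hold when named groups are left out, and makes no claim to rule out depression as an explanation. That is fair, but no other planned analysis addresses depression in Aim 6.

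One might also want the medication group widened to any mood-altering drug. That asks a different question, with unknown counts, and the documents do not require it.

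**Conclusion.** The point holds for Aim 6. Its only safeguards against confounding by depression are two separate exclusions of at most four people each, defined by a same-day SSRI dose and a reported diagnosis. No analysis uses the symptom score already collected. An unchanged result would be weak evidence against confounding by depressive symptoms.

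The size depends on assumptions. With correlations of 0.3 to 0.4 and 0.5 to 0.6, false positives stay at about 13% to 28% after the best possible exclusion of four, against about 5% with the covariate. Weaker correlations would shrink that gap. Whether symptoms confound any Aim 6 slope in these data is unknown.

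The documents do not support a claim that exposed people were in fact left in, that the checks cannot alter a result, or that the randomised comparisons are at risk.

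**What to change.** 1. In Aim 6, add a sensitivity version of model 2 with the session-1 depressive-symptom score (the nine-item questionnaire) as a covariate. Keep all 52 participants with complete data and report it beside the diagnosis exclusion.
2. As a secondary step, state which session the SSRI flag refers to. Base it on current SSRI use as recorded in the medication items already collected, not on a same-day dose alone.
3. Give the counts in each exclusion group by arm and their overlap, and state which aims the checks cover.

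Cost: wording in the amendment and one extra run per Aim 6 model, with no new data. The covariate uses one degree of freedom and leaves the detectable f² at about 0.157. It widens the slope's standard error by roughly 5% to 9% if symptoms correlate 0.3 to 0.4 with cytokine change, less any gain from lower residual variance. A wider SSRI flag may remove more than four people, and that number cannot be given from the documents. Because the data had already been accessed, the additions should be labelled as specified after access.
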